2.3 Other Agent(s): N/A

2.4 Rationale

Very few preclinical studies have combined IL-7 with PD-1 or anti-PD-L1 checkpoint blockade. One murine study showed the therapeutic efficacy of concomitant blockade of CTLA-4 and PD-1 relies on interdependence of IL-7 and IFN- γ signaling in T cells, predicting the exogenous IL-7 will boost the therapeutic efficacy [[Shi 2016](#)]. Another study of murine sepsis showed that IL-7 reverses immune suppression by increasing lymphocyte proliferation, expression of lymphocyte adhesion molecules, interferon-gamma production, and CD28 expression on splenic CD8+ T cells. Combined treatment with IL-7 and anti-PD-1 produced additive effects on CD28 expression, lymphocyte proliferation, and splenic secretion of interferon-gamma [[Shindo 2015](#)]. Of note, CYT107 therapy is currently being tested in human sepsis [ClinicalTrials.gov Identifier: NCT02640807]. In a recent Science paper [[Pauken 2016](#)] using the mouse model of chronic lymphocytic choriomeningitis virus (LCMV) infection explored the combined effect of IL-7 and anti-PD-L1 on the development and functionality of exhausted T cells. They confirmed that treatment with IL-7 starting in the effector phase can prevent development of T-cell exhaustion. By 8 to 11 weeks after treatment, however, the anti-PD-L1 reinvigoration of T cells was lost, and the quantity, proliferation, effector function, and inhibitory receptor expression of LCMV-specific CD8 T cells in the anti-PD-L1-treated mice were comparable to those in control-treated mice. Interestingly at this stage the combined treatment with IL-7 and anti-PD-L1, resulted in more antigen-specific CD8 T cells and improved coproduction of interferon- γ and tumor necrosis factor- α .

Atezolizumab induces remarkable responses in a subset of patients, yet the percentage of complete responses in the “all comers” population was only 5.5% and the median OS for all patients was only 7.9 months [[Package Insert 2017](#)]. Various mechanisms of immune escape, including (1) the lack of strong, tumor-specific antigens or epitopes recognized by T cells, (2) impaired or suppressed antigen presentation machinery including downregulation of major histocompatibility complex on cancer cells, (3) impaired or suppressed cytotoxic T-cell activation, (4) poor infiltration of T cells into the tumor microenvironment, and (5) increased immunosuppressive cytokines and cells in the tumor microenvironment prevent a large proportion of cancer patients from driving clinical benefit from anti-PD1/PD-L1 therapies [[Kim 2016](#)]. Thus, additional therapies to increase the frequency and depth of responses to atezolizumab are needed.

Atezolizumab has induced phenomenal lifesaving responses in some patients with advanced urothelial carcinoma, presenting an incredible foundation for building more effective regimens. The current trial will determine whether, by increasing the total body complement of T cells and expanding the T-cell repertoire, the addition of CYT107 to atezolizumab will improve upon the clinical benefit provided by atezolizumab alone.

2.5 Integrated Correlative Studies Background

2.5.1 Evaluation of peripheral CD4+ and CD8+ T-cell counts – Integrated Laboratory Correlative Study #1

As described above, CYT107 has been shown to double the number of peripheral blood lymphocytes including T cells. Thus, CD4+ and CD8+ T-cell numbers are important biomarkers for the effect of CYT107 on the peripheral T-cell populations. To assess the overall pharmacodynamic effect of atezolizumab plus CYT107 and to determine whether CYT107 in combination with atezolizumab results in the same, or different level, of expansion of peripheral lymphocytes, T-cell counts (both CD4+ and CD8+) will be evaluated in CLIA certified laboratories locally at each site. CD4+ and CD8+ T-cell counts will be evaluated at baseline, during treatment, and at end of therapy.

Hypothesis: The combination of atezolizumab with CYT107 will result in similar levels of peripheral blood T-cell expansion as with CYT107 alone.

2.5.2 Slide-Based Immune Phenotype Panel -- Multispectral IHC – Integrated Laboratory Correlative Study #2

Because tumor-infiltrating immune cells are associated with clinical outcomes, infiltrates from pre-treatment tumor tissue and from biopsies taken during treatment will be assessed by IHC to determine extent and the nature of T-cell infiltration and of the overall immune milieu of the tumor microenvironment (TME).

Paired baseline and post-baseline tumor biopsies will be evaluated using quantitative multicolor immunohistochemistry (IHC) with Perkin-Elmer's Vectra IHC platform. This platform employs spectral deconvolution imaging to separate optical signals from each antibody together with state-of-the-art image analysis capabilities to facilitate robust quantitative slide-based immunophenotyping. Using the Vectra multispectral imaging platform (PerkinElmer), adjacent tumor sections will be stained and imaged with a series of 5-6 antibodies per section simultaneously to investigate the spatial relationship between key immunomodulatory cell types and molecules. The antibodies will include, but are not limited to, the following: pancytokeratin (AE1/AE3), CD8, CD4, PD-1, PD-L1, CD68, CD163, FOXP3, arginase, and pan-MHC class I and class II. Data will be generated in the form of total positive cells, positive cells/mm², percentage positive cells in a population, ratios of cells and molecules of interest (e.g., PD-L1:CD8 or FOXP3+CD4+:CD8). Additionally, tumors may also be assayed by IHC for a variety of other markers including CD80, IFN-gamma CD3, CD5, TIA-1, CD20, CD11b, CD137, CD45RO, CD301CD56 and CD16 (natural killer [NK] and NK T cells), CD79a (B cells), GITR, TIM-3, FOXP3, LAG3. Furthermore, quantitative analysis of tumor-infiltrating lymphocyte (TIL) distribution (*i.e.*, stromal, and interface/invasive margin) will be performed. Anti-PD-L1 immunohistochemical staining will be performed at HistoGeneX (Naperville, IL) with the SP142 clone, in addition to the multispectral IHC (msIHC) to serve as both an independent test and control for the reproducibility of the msIHC assay. The study is intended to evaluate for changes in the immune profile of the tumor microenvironment. If sufficient archival tumor tissue collected before therapy is not

available, a baseline biopsy will be obtained before enrolling in the study as part of this protocol.

IHC studies will be performed under the direction of Dr. [REDACTED] at the Fred Hutchinson Cancer Research Center (Fred Hutch) Experimental Histopathology Laboratory, Seattle, WA, or other agreed upon investigator.

Hypothesis: The combination of atezolizumab with CYT107 will alter the TME (tumor microenvironment) towards a pro inflammatory phenotype.

2.5.3 Assessment of tumor biopsy by gene expression analysis -- Interferon γ (IFN γ) Gene Expression Signature - NanoString[®] nCounter[®] Human Immunology V2 Panel and the nCounter[®] PanCancer Immune Profiling Panel – Integrated Laboratory Correlative Study #3

To identify potential signatures correlating with tumor T-cell infiltration patterns and clinical response Tumor tissue will be tested for gene expression using NanoString[®] technology on unstained tissue formalin-fixed paraffin-embedded (FFPE) slide material. Specifically, slides will be analyzed using both a 770-gene panel (nCounter[®] PanCancer Immune Profiling Panel) which contains markers for 24 different immune cell types and populations, 30 common cancer antigens and genes that representing immune responses including checkpoint blockade genes as well as the NanoString[®] nCounter[®] Human Immunology V2 Panel which contain genes associated with the IFN γ Gene Expression Signature. These gene expression profiles may provide an additional detailed phenotype to guide correlative investigation.

NanoString[®]-based gene expression analysis, specifically for the IFN γ Signature, will be used to test the hypothesis that the investigational study treatment regimen, CYT107 plus atezolizumab, will promote a proinflammatory antitumor immune response. The IFN γ Signature, which is comprised of IDO1, CXCL10, CXCL9, HLA-DRA, STAT1 and IFN γ , has previously been shown to correlate with anti-PD1 response and nonresponse. RNA will be extracted from all paraffin-embedded tumor samples and analyzed using the NanoString[®] nCounter Immunology V2 Profiling Pane, which includes the aforementioned genes of the IFN γ Signature, as well as over 700 other genes associated with inflammation. The samples used will be taken from tissue sections adjacent to those stained for multispectral IHC to facilitate comparison between these analysis sets. Samples will consist of matched pre- and post-treatment FFPE biopsies.

These analyses will be performed in coordination with NanoString[®] Technologies in Seattle, WA, and analyzed using qualified analytic tools at the immunopathology lab of the Fred Hutch.

Hypotheses: The combination of Atezolizumab with CYT107 will alter the TME towards a pro inflammatory GEP phenotype, and distinct gene expression patterns will be identified that may correlate with clinical outcomes.

2.5.4 T-Cell Receptor Repertoire Analysis -- TCR sequencing – Integrated Laboratory Correlative Study #4

We will perform TCR sequencing where pretreatment and post-treatment biopsies are available. TCR repertoire analysis will be performed on RNA extracted from FFPE biopsies, and T cells isolated from PBMCs from the research blood collections throughout study participation. TCR repertoire analysis has been standardized and commercialized by Adaptive Biosciences. The TCR sequences will also specifically be queried for sequences already known to encode for TCRs reactive to shared antigens often expressed in urothelial transitional cell carcinoma (e.g., MAGE-A3, NY-ESO-1, LAGE-1, and PRAME).

Samples will be analyzed at Adaptive Bioscience in Seattle, WA, or other agreed upon vendor or collaborator.

Hypothesis: The combination of Atezolizumab with CYT107 will result in emergence and/or increased prevalence of specific TCR sequences reflecting the clonal expansion of antitumor T cells, and expansion of those specific T-cell clones in TILs (exhibited by higher TCR clonality) will be associated with improved response to therapy.

2.5.5 Tumor-Associated Neo-antigen discovery -- Whole Exome Sequencing and RNAseq and Antigen Prediction – Integrated Laboratory Correlative Study #5

In order to investigate the role of T-cell-mediated immunity directed towards tumor-specific mutant antigens, genomic sequencing and RNAseq of tumor cells from baseline tumor biopsy relative to non-tumor cells from whole blood (PBMC) will be performed to: i) identify tumor-associated neoantigens; and ii) identify the genomic variances that may contribute to response or disease progression and provide an understanding of molecular abnormalities.

DNA and RNA will be extracted from baseline or archival FFPE tumor biopsies will be sequenced to identify overexpressed known “shared” tumor-associated antigens (TAAs) and nonsynonymous expressed mutations using available and standard-of-practice technologies. For example, a computational approach (BIMAS and SYFPEITHI algorithms) can be utilized to analyze and prioritize these mutation-derived “virtual” antigens in terms of their likelihood to bind to/be presented by MHC I alleles (HLA-A2, A3, A24). Potential antigens can be encoded in tandem minigene constructs with intervening P2A viral sequences to allow for equimolar expression of multiple “long” (~27 amino acids) peptides centered on the putative antigenic mutational sites. These neoantigenic libraries will be cloned into an appropriate expression vectors to allow for in vitro- transcription of neoantigen-encoding mRNA for use in ELISPOT assays to detect neoantigen immune responses. RNAseq will also identify whether common “shared” antigens are also expressed, including MAGE-A3, NY-ESO-1, LAGE-1, and PRAME. Common epitopes sequences from these shared antigens will also be transduced as above. Quantitation of mutation burden may also be important for urothelial carcinoma, where

immunogenicity and/or responses to PD-1/PD-L1 axis-directed therapies may be associated with a high mutation burden.

These analyses will be performed using qualified analytes and analytic tools at the immunopathology lab at the Fred Hutch or at a vendor, to be determined.

Hypothesis: Clinical outcomes will correlate with neoantigen and mutational burden.

2.5.6 Antitumor Immune T-cell Responses – ELISPOT – Integrated Laboratory Correlative Study #6

If there are positive clinical responses, antigen-specific T-cell responses may be assessed by IFN γ enzyme-linked immunospot (ELISPOT) assay to provide information regarding the effect of the atezolizumab and CYT107 regimen on antigen-specific T-cell–functional antitumor responses. The ability of the investigational treatment to induce a tumor antigen-specific immune response will be assessed using ex vivo incubation of PBMC-derived T cells with autologous PBMC either pulsed with peptide antigens or recombinant proteins representing known ongoing and nascent antitumor responses (PRAME, NY-ESO-1, MAGE-A3 and/or p53), or neoantigens described above. Memory viral responses (influenza A, CEF) will also be assessed as controls. We will quantitate the strength of the antigen-specific T-cell responses and compare baseline and post-baseline T-cell responses for each putative antigen. The absolute change in ELISPOT responses for antigens will be compared between the SFC/million PBMC at baseline (before treatment initiation) and at designated time points post-treatment.

Assays will be performed in the CITN Immune Monitoring Laboratory (CIML) at the Fred Hutch under the direction of Dr. [REDACTED], or an agreed upon vendor or collaborator.

Hypothesis: The combination of atezolizumab with CYT107 will result in increased T-cell responses to known and/or neoantigens.

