2.2.2 Recombinant Glycosylated Human Interleukin-7 (CYT107)

A relatively nontoxic regimen of weekly IL-7 will substantially increase the total body complement of T cells of all phenotypes. The current trial will test whether addition of IL-7 to atezolizumab, using an IL-7 regimen known to increase the total body complement of T cells, will increase the frequency and depth of clinical responses to atezolizumab.

2.2.2.1 *Mechanism of action*

IL-7 is a homeostatic growth factor for T cells that normally contributes to maintaining the normal number of peripheral blood T cells. IL-7 is the T-cell equivalent of erythropoietin and thymopoietin with multiple functions that could increase the efficacy of atezolizumab. IL-7-mediated signaling can induce proliferation in the absence of T-cell receptor signaling [[Swainson 2007](#)]. IL-7 signals through the IL-7 receptor (IL-7R) heterodimer composed of the common γ -chain (CD132) cytokine receptor and a unique IL-7R α (CD127). During normal conditions, IL-7R expression is maintained on resting T cells [[Mackall 2011](#)] and endogenous IL-7 is continuously available in secondary lymphoid organs as a result of stromal cell IL-7 production [[Takada 2009](#)].

2.2.2.2 *Summary of Nonclinical Experience*

Exogenous IL-7 induces expansion of most categories of T cells. In preclinical and clinical studies IL-7 has been shown to:

1. Increase peripheral blood T cells by several fold with little toxicity [[Levy 2009](#); [Sportes 2010](#); [Perales 2012](#); [Tredan 2015](#); [Sheikh 2016](#)],
2. Expand all categories of T cells including CD8, CD4 and memory T cells [[Sportes 2010](#)],
3. Increase the total body complement of T cells including increased size of lymph nodes, spleen, liver [[Sportes 2008](#)],

4. Increase T-cell receptor (TCR) diversity by preferentially stimulating the growth of TREC positive, naïve T cells [[Sportes 2008](#)]. Continuous signaling by IL-7 induces antiapoptotic and costimulatory responses that are essential for the survival of naïve T cells.
5. Maintain effector T-cell function,
6. Increase the ratio of CD8+ T cells to Tregs, as IL-7R α expression is relatively low on FOXP3+ Treg cells compared with nonregulatory T-cell subsets [[Liu 2006](#); [Seddiki 2006](#)].
7. Increase tissue infiltration of T cells into gut mucosa (other tissues have not been examined) [[Sereti 2012](#)].
8. Reverse neutrophil lymphocyte ratios [unpublished data – CITN12-03 (NCT01881867)]

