9. Augment vaccine-induced cell responses in murine models [[Melchionda 2005](#)]
10. Augment immune-mediated control of both tumors and viruses [[Mackall 2011](#)].

After either T-cell activation, IL-7 signaling, or both, IL-7R α is down-regulated on terminally differentiated, senescent T cells [[Fry 2003](#)], [[Park 2004](#)] but becomes reexpressed after several days and remains expressed during the later contraction phase. IL-7R α is also selectively expressed on a small minority of effector T cells that are destined to enter the central memory T-cell pool, thus implicating IL-7 as a modulator of the effector to memory cell transition [[Kaech 2003](#)].

2.2.2.3

Summary of Clinical Experience

The CYT107 dose and regimen have been established in prior clinical trials. More than 380 patients have been exposed to CYT107. Weekly CYT107 \times 3 or 4 at doses of 10 to 20 μ g/kg can double the number of peripheral blood T cells (CITN Immune Monitoring Lab data). Both naïve and memory T cells are expanded by CYT107 with a peak of proliferation at day 7. Repeated doses of CYT107 induce expansion of CD4+ and CD8+ T cells subsets. Importantly, there is no significant difference between the 10 and 20 mcg/kg dose levels and biological effect on CD4+ and CD8+ T-cell number increases [[Levy 2012](#)], Figures 1A and 1B]. The increases last for weeks to months in some individuals [[Levy 2009](#)]. Extrapolating from the increase in size of lymph nodes, spleen, and liver with FDG-PET, the total body burden of T cells also increased correspondingly [[Sportes 2008](#)]. However, the 10 μ g/kg dose level is tolerated better, with no reported serious unexpected serious adverse reactions (SUSARs) reported compared to 4 cases reported at the 20 μ g/kg dose. Importantly, the 20 μ g/kg dose level has been associated with autoimmune adverse events, include Henoch-Schonlein purpura, lichen planus and the emergence of neutralizing antibodies [CYT107 Investigator's Brochure].

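### ELISPOT change per million PBMC can mix CYT107's nonspecific T-cell expansion with an antigen-specific response, and the planned comparison makes no use of the viral controls

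*Combined protocol and SAP*

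**What the plan says.** Section 2.5.6 aims to show whether treatment induces an immune response specific to tumor antigens, and hypothesizes that the combination increases T-cell responses to known antigens or neoantigens. The stated measure is the within-patient change for each antigen: "The absolute change in ELISPOT responses for antigens will be compared between the SFC/million PBMC at baseline (before treatment initiation") and at set times after treatment. On controls the section says only: "Memory viral responses (influenza A, CEF) will also be assessed as controls". The assay is described as "ex vivo incubation of PBMC-derived T cells with autologous PBMC either pulsed with peptide antigens or recombinant proteins", while the denominator is PBMC. Running it is conditional: "If there are positive clinical responses, antigen-specific T-cell responses may be assessed".

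On the drug, Section 2.5.1 says "CYT107 has been shown to double the number of peripheral blood lymphocytes including T cells", and Section 2.2.2.3 says weekly dosing "can double the number of peripheral blood T cells (CITN Immune Monitoring Lab data"). Section 2.2.2.2, item 2, says IL-7 has been shown to "Expand all categories of T cells including CD8, CD4 and memory T cells"; item 4 of the same list says naive cells are favored.

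Sections 9.1.6 and 13.5.2 add no normalization to T-cell number, no rule for using the viral controls and no between-arm ELISPOT comparison. Section 13 says there will be no separate SAP.

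**The concern.** A spot count per million PBMC depends on two things: how many T cells there are per million PBMC, and what fraction of them respond to the antigen. Only the second concerns antigen specificity. CYT107 is given to move T-cell numbers, and the expansion described is not antigen-specific. A rise in spots per million PBMC could therefore come from the drug's known pharmacology.

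The timing allows this. The Cycle 2 Day 1 ELISPOT draw is nominally day 29, seven days after the fourth injection on day 22. Section 2.2.2.3 places peak proliferation at day 7 and says the increases can last for weeks or longer in some patients. The control arm receives no CYT107, so a between-arm comparison of the same measure would not remove the effect.

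At stake is the interpretation of this correlative study: support for its hypothesis might not show an antigen-specific effect.

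**Working it through.** The protocol gives no ELISPOT sample size, threshold or expected effect, so there is no planned figure to reproduce. The check is a composition identity.

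**Inputs**
- k, the multiple by which T cells rise: 2 (Sections 2.2.2.3 and 2.5.1). This is a blood count, not a share of PBMC.
- p, the baseline T-cell share of PBMC: not given. Assumed 0.4 to 0.7.
- m, the multiple by which other PBMC rise: not given. Shown at 1, 1.5 and 2, because Section 2.5.1 speaks of lymphocytes including T cells.
- Whole PBMC plated, and an unchanged antigen-specific fraction per T cell.

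**Formula.** Spots per million PBMC are multiplied by k / [k·p + m·(1 − p)]. With k = 2 and m = 1 this is 2 / (1 + p).

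| p | m = 1 | m = 1.5 | m = 2 |
|---|---|---|---|
| 0.4 | 2/1.4 = 1.43 | 2/1.7 = 1.18 | 1.00 |
| 0.5 | 2/1.5 = 1.33 | 2/1.75 = 1.14 | 1.00 |
| 0.6 | 2/1.6 = 1.25 | 2/1.8 = 1.11 | 1.00 |
| 0.7 | 2/1.7 = 1.18 | 2/1.85 = 1.08 | 1.00 |

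**Absolute scale.** At p = 0.6 and m = 1, the spurious change is 0.25 times baseline: 0 spots gives 0, 10 gives +2.5, 50 gives +12.5, and 500 (a strong viral control, say) gives +125. The artifact scales what is already there. On the planned scale, a tumor antigen at 50 and a viral control at 500 shift by different amounts although nothing specific has happened to either. As ratios both are 1.25, and the difference of their logs is zero.

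**Per T cell.** Dividing by the T-cell share of the same sample (0.60 before, 2 × 0.60/1.60 = 0.75 after) gives 1.25 × 0.60/0.75 = 1.00. Uniform expansion then shows no change, and the same holds at every p.

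**Naive-skewed expansion.** If antigen-experienced cells multiply by a rather than k, the per-PBMC multiplier is a / [k·p + m·(1 − p)]. At p = 0.6, k = 2, m = 1 the denominator is 1.6. With a = 1.6 the inflation vanishes, and below 1.6 spots per million PBMC fall. At a = 1.6 the per-T-cell figure is 1.6/2 = 0.8, a fall caused by dilution. Neither denominator is sufficient alone. The contrast with viral memory responses cancels either distortion to the extent that both memory populations expand alike.

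**The case against.** The strongest objection is the assay description itself. If isolated T cells are plated at fixed number with antigen-pulsed PBMC, the T-cell share of PBMC does not affect the count and there is no artifact. That stands as a possibility. Section 2.5.6 pairs that description with a PBMC denominator, so the two need reconciling either way.

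It also stands that counting per million PBMC already removes most of a doubling in blood, that a rise in other PBMC shrinks the rest, and that naive expansion may work in the opposite direction. Safeguards exist too: influenza and CEF responses are assayed, and control-arm patients give ELISPOT blood at the same cycles. What is missing is a rule for using them.

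One can argue that more antigen-reactive cells per PBMC is a benefit in itself, since the rationale is to enlarge the T-cell pool. That is fair, and is a reason to report both scales. It does not make the per-PBMC change a measure of specificity.

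A reader might infer that assaying only when clinical responses occur selects responders. The documents do not support this. The condition reads most naturally as a trial-level trigger, and both calendars schedule the draws without regard to response. At trial level it restricts almost nothing: with both arms at the 14.8% rate in Section 13.2.1, the chance of no responder among 48 randomized patients is 0.852^48 = 0.0005.

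**Conclusion.** The point holds in a conditional form. The planned measure can inflate existing responses in the experimental arm by about 18% to 43%, provided whole PBMC are plated, T cells double, other PBMC stay constant, antigen-reactive T cells expand with the rest, and the baseline T-cell share is 70% to 40% (assumed). With a 1.5-fold rise in other PBMC, the same shares give 8% to 18%; with a doubling, nothing.

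Two stronger readings should not be drawn. One is that spots rise for every antigen: naive-skewed expansion leaves the net direction open. The other is that expansion alone creates a response where there was none: a baseline of zero stays zero.

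The impact is small. ELISPOT is optional, is last among the cell-associated studies in Section 9's priority list, and supports no primary or secondary conclusion. The change is still worthwhile because the existing schedule already collects most of what it needs.

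**What to change.** In Section 2.5.6:

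1. State which cell is plated and make the denominator match it.
2. Alongside spots per million PBMC, report spots per million CD3+ T cells. Preferably use the T-cell fraction of the plated sample. Otherwise use the same-visit immunophenotyping, noting that it is a whole-blood assay (Section 2.6.2) while ELISPOT may be run on cryopreserved PBMC (Section 9.1.6.3).
3. Within patient, contrast the tumor-antigen change with the influenza/CEF change on a ratio or log scale, with a preset offset for zero counts, and compare arms. Cancellation is exact without an offset and approximate with a small one.

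Both study calendars place ELISPOT, CD4/CD8 counts and immunophenotyping together at Day 1 of Cycles 1, 2 and 3, and the viral controls are already planned, so no new samples are required. The cost is wording, minor extra analysis and some added noise from the normalization.
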